### 1. Injected Target Lesions

The baseline for each individual injected target lesion is defined as the measurement prior to the first injection of that lesion. Specifically:

- For target lesions injected at W1D1, the baseline is defined as the measurement obtained prior to W1D1.
- For the injection of other accessible non-injected lesions when an injected tumor is clearly decreasing in size, the baseline measurement for these newly injected lesions is defined as the preceding measurement obtained

### Statistical Analysis Plan

Regeneron Pharmaceuticals Inc. / Protocol: CMP-001-010 IQVIA Biotech (Confidential) Project # RZA44091

- prior to the initial injection of these lesions and the baseline for these lesions will not be the measurement prior to W1D1.
- Baseline SOD is defined as the sum of diameters of the individual lesion at its respective baseline; thus, if a lesion is not injected until post W1D1, then the baseline for the injected SOD will take the data from different time points into consideration.
- Best change in tumor burden (i.e., maximal percentage reduction in SOD)
  will also incorporate measurement data from different time points,
  regardless of whether a lesion was injected after W1D1. However, only
  measurements taken after the initial injection can be considered for best
  response.

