- s. To be eligible, subjects must have progressive disease according to RECIST v1.1 within 12 weeks of the last dose of a PD-1 blocking antibody (either monotherapy or combination therapy). Disease progression on PD-1 blocking antibody must be confirmed by PI assessment using baseline imaging or imaging at the time of response and 2 consecutive scans 4 weeks apart demonstrating sustained progression. The confirmatory scan may serve as the Baseline for this study if completed within 30 days before the start of study treatment. Radiographic and/or photographic imaging must be submitted for BICR eligibility verification. If available, historic photographic imaging collected at screening may be used to verify subject eligibility. Subjects must have a minimum of one target lesion not intended for IT injections identified at baseline.
- t. Baseline CNS imaging by contrast-enhanced CT or MRI must be provided at Screening; on-study CNS imaging is required in presence of clinical symptoms or if CNS disease was present at Baseline.
- u. Disease assessments will be performed predose beginning at W13D1 (-7 days) and repeated every 9 weeks (-7 days) (eg, W22D1, W31D1, etc.). A response (complete response, partial response, immune complete response, or immune partial response [per RECIST v1.1 or immunotherapy Response Evaluation Criteria in Solid Tumors]) will be confirmed with follow-up disease assessments performed at least 4 weeks after the date of initial response. Disease assessments will continue every 9 weeks after the confirmatory scans. All scans should be performed at least 2 weeks after the most recent CMP-001 IT injection to account for injection-related pseudoprogression. Disease assessments may be performed every 12 weeks for subjects with a response continuing more than 1 year. Refer to Section 7.2. for Disease Assessments. If a CR is observed in a subject, sites should continue to obtain confirmation photographs at subsequent assessments.

TABLE OF CONTENTS

	ATOR'S AGREEMENT	
SPONSOR	PROTOCOL APPROVAL	3
PROCEDU	JRES IN CASE OF EMERGENCY	4
SYNOPSIS	35	
LIST OF T	ABLES	24
LIST OF F	IGURES	24
LIST OF A	BBREVIATIONS AND DEFINITIONS OF TERMS	25
1.	INTRODUCTION	28
1.1.	Background	28
1.2.	CMP-001	29
1.2.1.	Previous Clinical Studies With CMP-001	29
1.3.	Nivolumab	30
1.3.1.	Nivolumab Mechanism of Action	30
1.3.2.	Nivolumab Clinical Activity	30
1.3.3.	Benefit/Risk Assessment	30
1.4.	Study Rationale	31

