5.1.2. CMP-001

Subjects will receive CMP-001 10 mg weekly for 7 doses (W1D1 to W7D1), after which CMP-001 will be administered by IT injection Q3W (W10D1, W13D1, etc.). The first dose of CMP-001 may be administered SC or by IT injection, at the discretion of the Investigator; all subsequent doses are planned to be administered IT. On visits where both study treatments are administered, CMP-001 should be administered before nivolumab. There is no specified waiting period between the end of CMP-001 injection and the initiation of nivolumab infusion. CMP-001 should be administered until a reason for treatment discontinuation is reached (Section 4.5.). If treatment with nivolumab is permanently discontinued due to an immune related AE, treatment with CMP-001 must be discontinued. See Section 5.1.3. for dose modifications for CMP-001.

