5.1.2.3. CMP-001 Injections

5.1.2.3.1. Selection of Lesion for Injection

All Screening disease assessments (radiological and photographic images) must be submitted to a BICR in order to verify disease progression. The same disease assessment method (eg, CT, MRI) used during Screening should be used throughout the study for all disease assessments, whenever possible.

Eligible subjects must have at least 1 accessible lesion amenable to repeated IT injection. Cutaneous, SC, and/or nodal tumors that are visible, palpable, or detectable by ultrasound guidance are acceptable for IT injection.

Vigilance should be used when selecting lesions for injection that are in close proximity to critical structures (eg, major airways, major blood vessels).

Tumors should be at least 0.5 cm in longest diameter and need not be the largest measurable lesion. A visceral tumor may be injected with or without the use of interventional radiology if, in the opinion of the Investigator after discussion with the Medical Monitor, it is an appropriate additional site for IT injection. The preferred tumor for IT injection is an accessible lesion that is most rapidly progressing in the judgment of the Investigator.

When more than 1 tumor is amenable to IT injection, the Investigator may inject up to 3 tumors per CMP-001 treatment visit. The total dose of CMP-001 may be divided across the tumors at the Investigator's discretion, and the volume injected into each tumor must be recorded. If an injected tumor is clearly decreasing in size and another accessible non-injected tumor is not, then the Investigator may divide the CMP-001 dose between the 2 tumors or switch from injecting the regressing tumor to injecting the non-responding (or growing) tumor. However, there should always be at least 1 target lesion that will not be injected for each subject. These lesions not intended for injection may be located in any metastatic site.

Subjects with metastatic disease who have regression of all injectable lesions, or who have an injection site reaction that precludes injection of the tumor, should receive CMP-001 SC near an original tumor (peritumoral) or in the area of the draining lymph nodes (see Appendix G).

NOTE: Subjects must have a minimum of one target lesion not intended for IT injections identified at baseline.

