Disease status will be assessed by computed tomography (CT) or magnetic resonance imaging (MRI) and other appropriate measures beginning predose at Week 13 Day 1 (W13D1) and repeated every 9 weeks (eg, W22D1) while the subject is on treatment. All scans should be performed at least 2 weeks after the previous CMP-001 IT injection to prevent injection-related pseudoprogression. Imaging should not be delayed for delays in treatment. Disease assessments may continue every 12 weeks for subjects with a response lasting more than 1 year.

Responses (CR, PR, immune complete response [iCR], or immune partial response [iPR]) will be confirmed by a follow-up disease assessment performed at least 4 weeks after the initial response date, and at least 2 weeks after the last CMP-001 injection.

Subjects who discontinue study treatment should complete an end of treatment (EOT) visit and 100-day safety follow-up. Subjects who have stopped all study treatment but have not met criteria for study discontinuation should remain on study for post-treatment follow-up (PTFU) and long-term survival follow-up (LTSFU) and receive study evaluations for efficacy according to the Schedule of Assessments.

Note: 100DFU = 100-Day Follow-up; EOT = End of Treatment; IT = intratumoral; IV = intravenous; LTSFU = long-term survival follow-up; PTFU = posttreatment follow-up; Q3W = every 3 weeks; Q9W = every 9 weeks; Q12W = every 12 weeks; QW = every week.

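### CT/MRI-measured target lesions switched to injection at doses 2 to 8 because an injected tumor is shrinking have no baseline that the SAP permits

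*SAP*

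**What the plan says.** SAP section VIII.A, under Injected Target Lesions, opens with a general rule: "The baseline for each individual injected target lesion is defined as the measurement prior to the first injection of that lesion". Two specific cases follow. Lesions injected at W1D1 use the measurement before W1D1. The second case is introduced by "For the injection of other accessible non-injected lesions when an injected tumor is clearly decreasing in size". There, "the baseline measurement for these newly injected lesions is defined as the preceding measurement obtained" before the initial injection, and the same bullet ends by stating that "the baseline for these lesions will not be the measurement prior to W1D1". Later bullets say that the injected baseline sum of diameters (SOD) may combine lesions from different time points, and that only measurements after a lesion's initial injection count toward best change.

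On timing, SAP section II.A has disease status assessed "beginning predose at Week 13 Day 1 (W13D1) and repeated every 9 weeks". Protocol Table 1, footnote u, adds a window of 7 days before each assessment. Table 1 also schedules photographic assessment at Screening and again at W1D1. Protocol section 7.2.2 includes caliper measurements of superficial cutaneous lesions in that assessment.

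On switching, Protocol section 5.1.2.3.1 allows the Investigator, when an injected tumor is clearly shrinking and another accessible tumor is not, to divide the dose or to "switch from injecting the regressing tumor to injecting the non-responding (or growing) tumor". It sets no limit on which dosing visit this may happen at.

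**The concern.** The second case sets two conditions: the baseline is the last measurement before first injection, and it is not the one taken before W1D1. Both can hold only if something was measured after treatment began and before the switch. Until W13, no radiographic measurement is scheduled that would meet them.

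The baseline feeds three outputs: the injected baseline SOD, the best percentage change in injected SOD, and the within-subject waterfall of injected against non-injected target lesions (SAP section VIII.C). SAP section VIII.E cancels the itRECIST exploratory analyses, so these are the injected-lesion results that remain.

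A lesion without a baseline would not be missing at random, because it was chosen for injection after failing to respond. It may be lost on the other side too. Under Non-injected Target Lesions, the SAP treats non-injected response as non-evaluable once such a lesion is injected, and a lesion switched before W13 has had no scheduled on-treatment scan by then.

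**Working it through.** Inputs: CMP-001 doses 1 to 7 at W1 to W7, dose 8 at W10 and dose 9 at W13 (Protocol section 5.1.2 and Table 1); radiographic assessments at Screening, W13 (-7 days) and every 9 weeks after (Table 1, footnote u); scans at least 2 weeks after the latest intratumoral injection (Protocol section 7.2.4).

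**Step 1: calendar.** Study day = (week - 1) × 7 + 1.

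| Event | Study day | Latest scheduled radiographic measurement |
|---|---|---|
| Dose 2 (W2) | 8 | Screening |
| Dose 7 (W7) | 43 | Screening |
| Dose 8 (W10) | 64 | Screening |
| First on-study scan window | 78 to 85 | – |
| Dose 9 (W13) | 85 | W13 |

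Doses 2 to 8 are 7 visits, all before Day 78. Dose 9 is the first with a post-W1D1 scan available beforehand.

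**Step 2: apply both conditions to a CT/MRI-measured lesion switched in at doses 2 to 8.**
- Taking the Screening value satisfies the preceding-measurement condition but breaks the exclusion.
- Taking the W13 value satisfies the exclusion but comes after the first injection.
- Taking no value breaks the general rule that each injected target lesion has a baseline.

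The SAP gives no fallback.

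**Step 3: could an unscheduled scan help?** Protocol section 7.2.1 collects such scans. If every dose is intratumoral and on time, the 2-week rule leaves no compliant day from Day 2 to Day 56: dose 7 falls on Day 43, and 43 + 14 = 57. Days 57 to 64 comply, so an unscheduled compliant scan could serve dose 8 but not doses 2 to 7.

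**Step 4: who is outside the problem?**
- Superficial skin lesions: the W1D1 caliper value is not literally before W1D1 and precedes a first injection at dose 2 or later. Table 1 does not say that it is predose.
- Lesions first injected after W1D1 for another reason, such as a subcutaneous first dose or an injection site reaction: the exclusion does not reach them, and the general rule gives them the pre-W1D1 value.

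**Step 5: check against the SAP's source.** SAP section VIII.A attributes these definitions to itRECIST. Protocol Appendix F (Injected response) compares each injected lesion at its smallest with its size before first injection and does not exclude a pretreatment value. The conflict comes from the added clause.

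**Step 6: age of the value if the clause is removed.** A Screening measurement (Day -30 to Day -1) is 7 + 1 = 8 to 7 + 30 = 37 days old at dose 2, and 63 + 1 = 64 to 63 + 30 = 93 days old at dose 8.

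**The case against.** The strongest reply is that the intent is clear. The following bullet explains that late-injected lesions contribute baselines from different time points, so the clause may mean only that the W1D1 baseline is not carried over automatically. That is probably what was intended. The words are categorical, however, and a programmer who follows them has nothing to use.

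The reply also limits the reach of the point. The conflict needs a target lesion, measured by CT or MRI, switched in before W13, because another tumor is clearly shrinking. Protocol section 5.1.2.3.1 keeps at least one target lesion uninjected, and Appendix F says that designated non-injected target lesions should stay so as long as possible. There may be few such lesions, or none. All analyses are descriptive in 44 subjects. These limits stand.

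A reader might infer two stronger things. One is that every lesion first injected at doses 2 to 8 lacks a baseline. The exclusion is written only for regression-triggered switches, and skin lesions have the W1D1 assessment, so the documents do not support this. The other is that the rule would re-reference early-switched lesions to the W13 scan and hide shrinkage. With assumed sizes of 20 mm before W1D1, 12 mm at W13 and 10 mm at W22, best change would be (10 - 20)/20 = -50% from the pre-injection value and (10 - 12)/12 = -17% from W13. The SAP bars that choice, because baseline must precede the initial injection. The contrast describes a programming error and does not measure the effect of the rule.

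**Conclusion.** The contradiction is real and narrow. With dosing and imaging on schedule and no unscheduled scan, a CT/MRI-measured target lesion newly injected at doses 2 to 8 because an injected tumor is clearly decreasing has no permissible baseline. That covers 7 of the first 8 dosing visits. If dosing slips past the W13 scan, or a suitable unscheduled scan exists, the rule can be met.

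The consequence is loss of those lesions from the injected baseline SOD, the best change and the injected side of the waterfall. The loss is selective because the switch targets lesions that were not responding. The documents do not show which way this would move the injected-lesion result, since the lesions' course after injection is unknown, and they do not say how many were switched early. The primary confirmed ORR by BICR, DOR, PFS and OS do not use this baseline. The rule should be corrected before the injected-lesion outputs are produced, but it does not threaten the main results.

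**What to change.** In SAP section VIII.A, Injected Target Lesions, delete the closing clause of the second bullet ("the baseline for these lesions will not be the measurement prior to W1D1" and the conjunction before it). Replace it with: *For every injected target lesion, whatever the reason for injection, baseline is the most recent measurement obtained before that lesion's first IT injection, including the pre-W1D1 measurement when no later pre-injection measurement exists.*

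This wording keeps the W1D1 caliper value for a skin lesion first injected at dose 2 or later, provided that it was taken before that injection. It also agrees with the general rule and with Protocol Appendix F. Optionally, the lesion listing could flag baselines more than 9 weeks (63 days) older than the first injection, which would include any Screening value used at dose 8.

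The cost is one sentence of SAP text, with no new data and no change to how subjects are treated or imaged.

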### 2. Non-injected Target Lesions

- As long as the non-injected target lesions remain non-injected, the SOD for the non-injected target lesions will be compared against the measurement obtained prior to W1D1.
- If any non-injected target lesions are decided to be injected, then the maximal non-injected effect has been achieved and any subsequent non-injected response is considered non-evaluable.

The injection status of a target lesion will be determined based on the response to the Type of Injection question of the CMP-001 Dosing page. If 'Intratumoral (IT)' is selected at a specific time point, then the lesion is considered injected from that time point onwards and deemed non-injected prior to that injection time point. Once injected, the lesion will be considered an injected target lesion for all subsequent time points, even if not injected later on.

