7.2.1. Radiographic Imaging

Contrast-enhanced CT and MRI are the preferred radiographic imaging modalities for disease assessment. Contrast-enhanced CT imaging is required when contraindications are not present. Contrast-enhanced CT assessments may be combined with positron emission

tomography (PET) as long as disease status can be thoroughly assessed. Ultrasound imaging may be used for measurement of lesions for itRECIST.

Any additional imaging that may demonstrate tumor response or progression (including scans performed at unscheduled timepoints and/or at an outside institution) should be collected for RECIST 1.1 tumor assessment and submitted to the BICR.

A target lesion(s) not intended for intratumoral injections should be clearly labeled in the baseline imaging.

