The goal of IT RECIST (itRECIST) is to create guidelines for capturing data and assessing response in IT immunotherapy trials. As with iRECIST, the standardized data collection and initial suggestions for response assessment of itRECIST will be refined based on collected data. We anticipate itRECIST will initially be used for exploratory analyses, with primary and secondary end points based on RECIST 1.1, until evidence indicates that itRECIST improves efficacy assessment.

itRECIST

itRECIST is designed to address the unique needs of IT immunotherapy trials but, where possible, aligns with RECIST 1.1 and iRECIST. It does not dictate which lesions to inject at each visit, but rather provides guidelines for assessing responses as treatment evolves. The key questions, and the approaches to answering them, are as follows:

- 1. What is the overall response? Overall response is determined as per RECIST 1.1 (or per iRECIST, after initial progression).
- 2. What is the maximal effect of IT therapy (with or without systemic therapy) on noninjected lesions? The smallest (nadir) total size of predesignated noninjected lesions is compared with pretreatment size.
- 3. What is the effect of therapy on injected lesions? During treatment, an iterative assessment accounts for changes in lesions selected for injection. After treatment, a combined response compares the smallest size achieved by each injected target lesion with its size before injection.

It is important to define a lexicon of precise and simple terms for these criteria; novel, nonintuitive terminology hinders understanding and adoption. Therefore, lesions are classified as injected or noninjected, and the terms *injected response* and *noninjected response* describe response in injected and noninjected lesions, respectively. The choice not to use the term *abscopal effect* was deliberate, because this implies causality: injecting lesion A causes a response in lesion B. Many IT immunotherapies are administered with systemic immunotherapies; hence, noninjected lesions may be affected by systemic therapy alone.

LESION MEASUREMENT

Lesion measurements should be performed per RECIST 1.1, with one exception. Briefly, either computed tomography (CT) or magnetic resonance imaging should be used to measure target lesions. For skin lesions, RECIST 1.1 recommends color photography documentation, including a size standard or caliper for scale.

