## II. Study Design

### A. Design Overview

This is a multicenter, open-label, exploratory Phase 2 clinical study of CMP-001 IT in combination with Nivolumab IV in subjects with unresectable or metastatic melanoma refractory to PD-1 blockade. Eligible subjects must have confirmed disease progression during or within 12 weeks of their last dose of therapy containing a PD-1 blocking antibody for the treatment of unresectable cutaneous melanoma prior to enrollment. All subjects will receive CMP-001 IT and Nivolumab IV according to the Schedule of Assessments (Protocol Table 1) until a reason for treatment discontinuation is reached.

CMP-001 10 mg IT will be administered weekly for 7 doses, after which it will be administered Q3W until the subject meets a condition for discontinuation of study treatment. The treatment will be given for a maximum of 2 years from the start of the study treatment. The first dose of CMP-001 may be administered SC or by IT injection, at the discretion of the Investigator; all subsequent doses are planned to be administered IT. The initial 7 CMP-001 doses on a weekly schedule must be completed before moving on to the Q3W CMP-001 dosing schedule.

If all injectable tumors regress, CMP-001 may be injected SC in the region of prior tumors or draining lymph node bed, at the Investigator's discretion (see Protocol Appendix F). On visits where both study treatments are administered, CMP-001 IT should be administered before Nivolumab. CMP-001 should be administered

Regeneron Pharmaceuticals Inc. / Protocol: CMP-001-010 IQVIA Biotech (Confidential) Project # RZA44091

[figure not shown]
until a reason for treatment discontinuation is reached, or for a maximum of 2 years from the start of the study treatment. See Protocol Section 5.1.3. for treatment modifications for CMP-001.

Objective responses will be assessed by BICR and Investigator assessment according to RECIST v1.1. Subjects who continue study treatment beyond PD according to RECIST v1.1 at the discretion of the Investigator will be evaluated by the Investigator according to iRECIST.

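### The SAP's date-based injection status can make non-injected response non-evaluable before the first scheduled scan, although the target lesion reserved at baseline is never injected

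*SAP*

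**What the plan says.** **Status rule.** In SAP VIII.A, under Non-injected Target Lesions, "The injection status of a target lesion will be determined based on the response to the Type of Injection question" on the CMP-001 Dosing page. From the first record of an IT injection, "then the lesion is considered injected from that time point onwards and deemed non-injected prior to that injection time point".

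**Trigger.** The same subsection says "If any non-injected target lesions are decided to be injected", the maximal effect is taken as reached and "any subsequent non-injected response is considered non-evaluable". Nothing there ties the non-injected set to a designation made at baseline.

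**Dosing and scans.** SAP II.A states "The first dose of CMP-001 may be administered SC or by IT injection, at the discretion of the Investigator". Later doses are planned IT, weekly to W7 and every 3 weeks from W10. The first scheduled scan is predose at W13D1, with a window of up to 7 days earlier (Protocol Table 1, footnote u).

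**Baseline designation elsewhere.** Protocol Appendix F answers the non-injected question this way: "The smallest (nadir) total size of predesignated noninjected lesions is compared with pretreatment size". It assigns target-injected (T-I) and target-non-injected (T-NI) lesions at baseline and ends evaluability once a T-NI lesion is injected. Protocol 5.1.2.3.1 requires at least one target lesion per subject that is not injected, and Protocol 7.2.1 adds: "A target lesion(s) not intended for intratumoral injections should be clearly labeled in the baseline imaging".

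**Endpoint.** Response in non-injected target lesions by BICR is a secondary endpoint (Protocol 2.2.2; SAP V.B). SAP VIII.A and VIII.C derive its ORR with the approach used for the overall ORR.

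**The concern.** The status rule and the trigger are each understandable alone. Together they treat a lesion planned for injection as a non-injected lesion until its own first IT dose, and then treat that dose as the loss of the non-injected set. Whether a subject can be assessed for systemic response would then depend on the route of dose 1 and on the order in which planned lesions are injected, not on what happened to the lesion held in reserve.

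If the rule is programmed literally, some subjects have no evaluable scheduled post-baseline assessment for a secondary endpoint. If they stay in the ITT denominator, the reported rate is pulled down for a reason unrelated to treatment. The waterfall plot in SAP VIII.C comparing injected and non-injected target lesions relies on the same status rule. No itRECIST analysis is available as a check, because SAP VIII.E records that investigator itRECIST data were not collected.

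**Working it through.** The plan gives no figure for this endpoint, so there is none to reproduce. The check applies the rules to the calendar and then illustrates the size.

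**1. Calendar.** CMP-001 visits before W13D1 are W1 to W7 and W10, 8 visits in all. Without W1D1, 8 − 1 = 7 visits remain (W2 to W7 and W10) at which a target lesion can be injected for the first time before the first scheduled scan. The 7-day window moves that scan to W12D1 at the earliest, which is still after W10D1.

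**2. Rules applied to cases.** Lesion A is a target lesion planned for injection, B is the reserved target lesion, and C is a second planned target lesion.

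| Case | SAP VIII.A as written | Appendix F |
|---|---|---|
| Dose 1 SC; A first injected IT at W2D1; B never | Non-evaluable from W2D1 | Evaluable |
| Dose 1 IT into A; C first injected at W3D1; B never | Non-evaluable from W3D1 | Evaluable |
| Dose 1 SC; only non-target lesions injected later | Evaluable | Evaluable |
| Dose 1 SC; A first injected after the scan at W13D1; B never | W13 scan evaluable, later scans not | Evaluable |
| B itself injected at W4D1 | Non-evaluable | Non-evaluable |

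The first two rows are the defect: the rules disagree and no scheduled scan is evaluable under the SAP. The third shows that the lesion injected must be a target lesion. The fourth falls outside this point because the first scan is kept. In the fifth the two rules agree.

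The first two rows are realistic. Protocol 5.1.2.3.1 allows up to 3 tumors per visit and changes of injected lesion, and the SAP's own section on injected target lesions provides for lesions first injected after W1D1.

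**3. Illustration of size.**

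- N = 44 (SAP II.C).
- Assumed true non-injected ORR p = 20%.
- Assumed: non-evaluable subjects remain in the denominator as non-responders.
- Assumed: response is independent of being affected.
- Affected share s: not in the documents, so a range is shown.

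Expected reported ORR = p × (1 − s).

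| s | Subjects affected (44 × s) | Expected reported ORR |
|---|---|---|
| 10% | 4.4 | 0.20 × 0.90 = 18% |
| 25% | 11 | 0.20 × 0.75 = 15% |
| 50% | 22 | 0.20 × 0.50 = 10% |

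**4. Dependence on independence.** The expected number of responders is 0.20 × 44 = 8.8. If none of them is affected, they fit among the 33 unaffected subjects at s = 25%, or the 22 at s = 50%, and the reported rate stays at 20%. The table is therefore an expectation under independence, not a bound.

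**The case against.** The best defense is that the SAP introduces these definitions by citing the itRECIST publication, where non-injected lesions are designated at baseline. The trigger can also be read as a change of plan for a reserved lesion, and the protocol does require such a lesion to be identified at baseline. A programmer who knows itRECIST could arrive at the right derivation. That reading is possible, but the sentence that sets status says something else, and SAP I.B states that the SAP governs where it differs from the protocol.

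Other parts of the objection stand and limit the point:

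- A reader might infer that an SC first dose alone makes a subject non-evaluable. It does not. A target lesion must then be injected IT, and injected tumors need be only 0.5 cm (Protocol 5.1.2.3.1), while measurability starts at 1 cm (Protocol Appendix D).
- A reader might count every switch of injected lesion as an error. Where the newly injected lesion was designated non-injected, loss of evaluability is what Appendix F intends.
- Scoring non-evaluable subjects as non-responders is an inference. SAP VIII.A gives that status to subjects who discontinue before a scan and does not address lesion-level non-evaluability.
- The label is shown to exist on images. SAP VI.A names eCRFs and central laboratory transfers as data sources, so the label may not yet be a data field.

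**Conclusion.** The point holds in this form: as written, SAP VIII.A makes non-injected response non-evaluable before W13D1 for a subject whose planned target lesion is first injected IT at any visit from W2D1 to W10D1, even when the reserved target lesion is never injected. This is a stated rule that gives the wrong result for a secondary endpoint and conflicts with Appendix F; it is more than a missing detail.

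The size is unknown, because the documents do not say how many of the 44 subjects are affected. The fall from 20% to 18%, 15% or 10% rests on the assumptions listed above, and the loss is smaller if affected subjects respond less often than the others. That is plausible for some of them, since Protocol 5.1.2.3.1 permits switching toward a tumor that is not responding.

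A reader might infer that the trial's main efficacy conclusion is at risk. The documents do not support that. The endpoint is one of several secondary ones, SAP II.C makes all analyses descriptive and exploratory, and the primary ORR does not use this rule.

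**What to change.** Revise the Non-injected Target Lesions text in SAP VIII.A to say that:

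1. The non-injected set is fixed once: the BICR target lesions designated at baseline as not intended for injection, found by matching the baseline image label to the BICR target lesion list.
2. Non-injected response becomes non-evaluable only from the first IT injection of a lesion in that set. The Dosing page is used only to detect that event.
3. The first injection of a target lesion outside the set, at any visit, does not change evaluability.
4. Non-evaluable subjects stay in the ITT denominator as non-responders, and their number is reported.

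Use the same set for the injected versus non-injected waterfall plot in SAP VIII.C.

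The cost is small but not zero: a few sentences, one derivation flag, and a mapping of the image label to the BICR lesion list as a data field. The protocol requires only one such lesion per subject, so the mapping should confirm that the label covers every target lesion meant to stay non-injected. It should be made from baseline material alone. Only the analysis definition changes; dosing and the choice of lesions to inject do not.
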